## **Study Sample**

Children eligible for study participation were 8- to 12-years old, in second, third or fourth grade at the time of recruitment and attended an elementary school in one of two school

districts that volunteered to participate in the study. One school district with a kindergarten through grade 12 enrollment of about 10,000 students is located in a suburban area, includes ten elementary schools, plus one parochial school and was a recruitment and intervention site from 2014-2017. The other school district with a kindergarten through grade 12 student enrollment of approximately 37,000 is located in an urban area, includes 43 elementary schools and was a recruitment and intervention site from 2016-2018.

Eligible children were required to have a BMI  $\geq$  75th percentile, calculated using the child's height and weight, as reported by the parent, school nurse or health care provider. Studies suggest that young children in the top quartile of the growth chart are at risk for excess weight gain during the early school years and intervention during this time may be critical to preventing excess weight gain. Other inclusion criteria were child and parent able to read, write and speak English, child living with participating parent most of the time and willingness to be randomized to the intervention or the attention control condition. Exclusion criteria included plans to move outside the school district within the next 12 months, child with food allergies, physical limitations or medical conditions that would limit the child's ability to participate in physical activity and emotional health conditions that would limit the child's ability to participate in group activities with other children. Only one child per household was allowed to participate in the study.

All adult participants were required to provide written consent for self and child for study participation. Children were required to provide written assent. To allow time for review, consent forms were mailed to the parent prior to the baseline measurement visit. The consent process was completed at the first measurement visit and before baseline data collection.

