### **Child and Parent Anthropometry**

Research staff collected child and parent height and weight using standardized procedures. BMI percentiles and BMI z-scores for child's gender and age were calculated using the 2000 Centers for Disease Control and Prevention (CDC) growth charts. The study's primary outcome measure was child age- and gender-adjusted BMI z-score. We also measured parent and child body fat percentile using a Tanita TBF-300A body composition analyzer scale. All anthropometric measures were collected at baseline, post intervention and follow-up.

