### Statistical Analyses

The primary outcome, child BMI-z at post intervention, was compared between intervention and control groups using general linear mixed model controlling for a blocked partially clustered design (intervention group only) via a random effect, adjusting for baseline BMI-z, child age, sex and puberty scale. Model diagnostics included assessment of conditional standardized residuals, normal probability and quantile-quantile plots and influence diagnostics using graphical procedures and influence statistics. Child BMI-z at follow up and percent body fat at post-intervention and follow-up were modeled in similar manner as the primary outcome. A priori power analyses estimated a minimal detectable treatment group effect size of 0.25 for age- and sex-adjusted BMI-z at 80% power with a sample size of 114 children or 57 per treatment group.

An adjustment for the partially clustered design was not performed for dietary and activity outcomes given small realized cluster sizes within the intervention group. The Healthy Eating Index, added sugars, energy, fat and saturated fat were modeled using general linear models; fruit, vegetable, fruit and vegetable juice and sugar-sweetened beverages were analyzed using marginalized two-part models; all models adjusted for baseline value, child percent body fat, sex and economic assistance. Sedentary and physical activity outcomes were modeled using generalized linear models (beta regression) adjusting for baseline value, child percent body fat, sex and age.

A two-sided type I error rate of 5% and 95% confidence intervals were used to assess statistical significance. For secondary outcomes, no adjustment for multiple comparisons was performed as analyses were considered supportive of the primary analysis and exploratory in nature. No modifications or imputations were made to the database, with the exception of accelerometer data. SAS software 9.4 (SAS Institute Inc., Cary, NC, USA) and R software were used.

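### Does a minimal detectable effect of 0.25 with 57 children per arm contradict the SAP's own numbers?

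*SAP*

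**What the plan says.** The only planning figure for the primary outcome is in the first paragraph of the SAP's Statistical Analyses section: "minimal detectable treatment group effect size of 0.25 for age- and sex-adjusted BMI-z at 80% power with a sample size of 114 children". The two arms are of equal size, 57 each. The same section sets the error rate: "A two-sided type I error rate of 5% and 95% confidence intervals were used to assess statistical significance".

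The primary model is described just before the power sentence. It is a linear mixed model for post-intervention BMI-z, "adjusting for baseline BMI-z, child age, sex and puberty scale", that accounts for a "blocked partially clustered design (intervention group only) via a random effect".

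Two protocol statements bear on the scale. Under Child and Parent Anthropometry, the "primary outcome measure was child age- and gender-adjusted BMI z-score". Under Study Sample, "Eligible children were required to have a BMI" at or above the 75th percentile, which narrows the spread of BMI-z in the sample.

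Neither document gives the unit of 0.25, the assumed SD, the baseline correlation, the ICC or cluster size, or a dropout allowance for the power calculation.

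**The concern.** An effect size quoted without units is usually taken as a difference in SDs. On that reading, the textbook two-sample formula needs 252 children per arm to detect 0.25, not 57, and the stated figure seems about twice as favourable as it should be. The outcome invites confusion because it is itself a z-score: a quarter of a BMI-z point and a quarter of this sample's SD are different quantities if the eligibility rule makes that SD well below 1. The power sentence also shows no allowance for the intervention-arm clustering that the primary model includes.

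If the figure were wrong, a reader of a null result might believe that the trial had 80% power against effects of 0.25 SD when it had much less.

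**Working it through.** **Inputs from the SAP.** Two-sided alpha 5%, power 80%, 57 per arm, stated detectable effect 0.25.

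**Assumed inputs, shown as ranges.** SD of BMI-z, baseline-to-12-month correlation r, ICC of the adjusted outcome in the intervention arm, number of intervention groups, dropout.

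**Step 1: unadjusted, unclustered, SD units.** Detectable effect = (1.960 + 0.842) × √(2/57) = 0.525, or 0.529 with the noncentral t. Power for 0.25 is 26.6% (normal) or 26.3% (t). This does not reproduce the SAP's figure. One-sided testing does not either (0.47), nor does reading 0.25 as Cohen's f, which equals d = 0.5 and needs 63 per arm.

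**Step 2: SD units with baseline adjustment.** Adjustment multiplies the SD by √(1 − r²). Setting 0.529 × √(1 − r²) = 0.25 gives r = √(1 − 0.472²) = 0.88. By assumed r (normal approximation, no clustering):

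| r | Detectable effect | Power for 0.25 |
|---|---|---|
| 0 | 0.525 | 27% |
| 0.70 | 0.375 | 46% |
| 0.80 | 0.315 | 60% |
| 0.85 | 0.276 | 72% |
| 0.88 | 0.249 | 80% |
| 0.90 | 0.229 | 86% |

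**Step 3: BMI-z points.** The residual SD that gives 0.25 at 57 per arm is 0.25/0.529 = 0.472 (0.476 by the normal formula). Many combinations yield it: a raw SD of 0.6 with r = √(1 − (0.472/0.6)²) = 0.62, or a raw SD of 0.8 with r = 0.81.

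**Step 4: clustering in the intervention arm only.** The protocol's site and cohort description suggests about 9 intervention groups, though it also permits 11; 9 is assumed here. Mean group size is 57/9 = 6.33. The inflation of the detectable effect is √{[(1 + 5.33 × ICC) + 1]/2}, which is 1.065 at ICC 0.05 and 1.125 at ICC 0.10. The required r becomes 0.90–0.91 in SD units. The required residual SD becomes 0.472/1.065 = 0.44 down to 0.472/1.125 = 0.42 in BMI-z points.

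**Step 5: an illustrative SD.** A standard normal cut at the 75th percentile has SD 0.492. This is only a guide: eligibility used reported height and weight, and the outcome is measured a year later. Detectable effects in BMI-z points:

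| r | No clustering | ICC 0.05 | ICC 0.10 |
|---|---|---|---|
| 0 | 0.260 | 0.277 | 0.293 |
| 0.5 | 0.226 | 0.240 | 0.254 |
| 0.7 | 0.186 | 0.198 | 0.209 |

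On this SD, 0.25 is met once r reaches about 0.28 without clustering (√(1 − (0.25/0.260)²)), 0.43 at ICC 0.05 and 0.52 at ICC 0.10. If 15% are also lost, each entry is multiplied by √(1/0.85) = 1.085, so the r = 0.7 row becomes 0.202, 0.215 and 0.227.

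**The case for a change.** The strongest case for a change is that this is the only planning number for the primary outcome, and nobody can reproduce it from what is printed. Its two natural readings may differ about twofold. The sentence shows no allowance for a random effect that the model contains. It does not say whether 114 is randomized or evaluable, although missing BMI-z values are not imputed. In SD units the figure needs a high correlation: at r = 0.80, power for 0.25 is 60% without clustering and about 51–55% with ICC 0.05–0.10 and 9 groups. One or two sentences would settle all this.

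The omission is real and that part stands. Three things do not follow from it.

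- **An arithmetic error.** The 26% and 0.53 figures assume SD units and r = 0, whereas the planned model adjusts for baseline BMI-z.
- **A bias in one direction.** In BMI-z points, with an SD near 0.49 and a moderate r, the stated 0.25 is conservative. In SD units with r below 0.88 it is optimistic. The documents do not decide between these readings.
- **A consequence for interpretation.** The SAP reports 95% confidence intervals, and these show which effects a null result leaves open, whatever was assumed at planning.

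**Conclusion.** The concern does not hold as an error. The stated 0.25 with 57 per arm is compatible with the planned adjusted model if r is about 0.88 in SD units, or the residual SD about 0.47 in BMI-z points. With assumed ICCs of 0.05–0.10 and about 9 groups, those become about 0.90–0.91 and 0.42–0.44. All these SDs, correlations, ICCs and group counts are assumptions, because the documents give none for the power calculation. The figure is therefore unverifiable rather than wrong, and 26% should not be presented as the trial's power.

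What remains is a reporting gap: the unit and the inputs were not written down. Both documents describe recruitment in the past tense, so the sentence no longer governs enrolment. Filling the gap would leave the primary model, the error rate, the estimate and its interval as they are. No change to the plan is called for.

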## **Study Aims**

The primary and secondary aims of the study were as follows:

**Primary Aim:** To test the efficacy of an elementary school-based, school nurse-led healthy weight management program to reduce excess weight gain among children, 8- to 12-years old with a body mass index  $\geq 75^{\text{th}}$  percentile, by increasing healthy dietary practices and physical activity levels and decreasing sedentary practices. We hypothesize that relative to the attention control condition, children receiving the intervention will have a significantly lower BMI, following implementation of the 9-month intervention, controlling for baseline values.

**Secondary Aim 1:** To examine the effects of the intervention on change in the weight-related behaviors of children. We hypothesize that the intervention will result in decreased consumption of sugar-sweetened beverages and energy-dense, low-nutrient foods, increased levels of moderate to vigorous physical activity, decreased sedentary behavior, and increased fruit and vegetable intake.

**Secondary Aim 2:** To examine the effects of the intervention on family lifestyle practices overseen by parents. We hypothesize that the effects of the intervention on family lifestyle practices overseen by parents, such as home availability of healthful foods, limits on screen time, frequency of family meals, will be more prevalent among families randomized to the intervention.

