### **Child Physical Activity**

Child physical activity was assessed at baseline and post intervention with the ActiGraph uniaxial accelerometer, validated for use in children. The ActiGraph was worn at the right hip for a 7-day period; four days of complete data were required for analyses. Counts were classified into intensity categories of sedentary, light, moderate, vigorous and moderate to vigorous physical activity (MVPA) using age appropriate count cutoffs. We also calculated number and average length of MVPA bouts. Trained research staff fit the Actigraph to the child, as per standard protocols.

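### Does naming beta regression for the activity outcomes leave the bout measures with a model that cannot be fitted?

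*SAP*

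**What the plan says.** The SAP, Statistical Analyses, gives the activity domain one sentence: "Sedentary and physical activity outcomes were modeled using generalized linear models (beta regression) adjusting for baseline value, child percent body fat, sex and age". It does not list the outcomes covered, state their scale or say what happens to a value of exactly 0.

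The protocol, Child Physical Activity, sorts accelerometer counts into five intensity categories (sedentary, light, moderate, vigorous and MVPA) and then adds: "We also calculated number and average length of MVPA bouts". The activity hypotheses are in Secondary Aim 1 (Study Aims), which expects "increased levels of moderate to vigorous physical activity, decreased sedentary behavior, and increased fruit and vegetable intake". Bouts do not appear there.

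On the standing of the secondary outcomes, the SAP says that "no adjustment for multiple comparisons was performed as analyses were considered supportive of the primary analysis and exploratory in nature".

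**The concern.** The beta distribution has support on the open interval from 0 to 1. A share of wear time fits that; a number of bouts or a mean length in minutes does not. The protocol describes the bout measures under its part on assessment and outcome measures, and the SAP offers one model family for activity with no alternative. Read literally, two of seven derived measures (five intensity categories plus two bout measures) could not be analyzed as planned.

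There is a second worry at the boundary. A child with no recorded vigorous activity has a share of exactly 0. If such children fell out of the model, they would be excluded because of their outcome, and the vigorous-activity comparison would lean towards active children. The SAP's dietary models make the silence more noticeable, because two-part models were chosen there for the intake of some foods and beverages.

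**Working it through.** The plan gives no figure on this point, so there is nothing to reproduce. The check has two parts: what the model can accept, and what the documents assign to it.

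**1. What the model can accept**

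The beta density with shapes a and b is proportional to y^(a−1) × (1−y)^(b−1) for 0 < y < 1. With a = 5 and b = 95 (assumed, mean 5/100 = 0.05), the log-density is minus infinity at each of 0, 1, 6 and 7.5.

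A beta regression with a treatment term was then fitted to simulated data for 114 children, 57 per group (the SAP's planned size). All outcome values are assumed, for illustration only.

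| Simulated response | Range | Result |
|---|---|---|
| MVPA as a share of wear time | 0.010 to 0.143 | fitted |
| Number of bouts | 1 to 13 | rejected by the software |
| Mean bout length, minutes | 5.1 to 18.8 | rejected by the software |
| Mean bout length divided by 60 | 0.085 to 0.313 | fitted |

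So the model works for shares and refuses bout measures in natural units. It accepts a rescaled bout length, but the SAP describes no rescaling. In this check, misapplication to raw bout values produced an error and not a wrong estimate.

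**2. What the documents assign to it**

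- The SAP sentence does not claim to cover every activity variable. It is also written in the past tense, as a report of models that were fitted. That implies responses between 0 and 1, and shares of wear time are the natural reading.
- The protocol says the bout measures were calculated. It does not say they were compared between groups.
- Secondary Aim 1 names MVPA and sedentary behavior, and both can be expressed as shares of wear time.
- The SAP does not give a model for everything collected. The pediatric quality-of-life inventory and the psychosocial factors, each with its own protocol section, have none. Silence on bouts is therefore weak evidence that beta regression was meant for them.

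**3. Exact zeros**

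The protocol requires four complete days of accelerometer data. A zero share of vigorous activity would thus mean no vigorous time recorded on any of the days used. The documents do not say how many children, if any, were in that position. Vigorous activity alone is not a named hypothesis; MVPA is, and it is zero only if moderate activity is absent too. The SAP also says that accelerometer data were the one exception to its rule of no modification or imputation. It does not say what was done, so this neither shows nor rules out a boundary adjustment.

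**The case for a change.** The best case for acting is reproducibility. Activity is a hypothesized effect, and a second analyst working from the SAP alone could not be sure which activity measures were modeled, on what scale, or with what rule for zeros. Rescaling bout length does not settle it: neither bout measure has a natural maximum in the documents, so the divisor would be arbitrary. A child with no bouts has a count of 0 and no defined mean length. The remedy would be a few sentences and no new data.

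Most of this stands as a remark on completeness. It does not show an unsuitable model, because the step from an unlisted set of outcomes to a model imposed on bouts is an inference. The exclusion bias is conditional on zeros that nobody has counted. Part of the obvious remedy would also need care: adding block or intervention-group terms to new bout models would contradict the SAP's statement that activity outcomes were not adjusted for the partially clustered design.

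**Conclusion.** The concern does not call for a change. It is correct that a count and a duration in minutes lie outside the support of the beta distribution, and that the SAP leaves the outcome list, the scale and the handling of zeros unstated. It is not established that beta regression was assigned to the bout measures, or that any child was lost at the boundary.

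This is a gap that a competent analyst fills sensibly: model the intensity categories as shares of wear time, deal openly with any zeros, and treat bouts as descriptive or use a model for counts and durations. The two-in-seven count holds only if every derived measure is taken to be a tested outcome, which the documents do not say.

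The conclusion rests on two assumptions: that the modeled activity outcomes were shares of wear time, which the choice of model implies but the SAP does not state, and that exact zeros were absent or few. If many children had no vigorous activity, the rule for zeros would matter for that one exploratory comparison. The BMI z-score analysis would be unaffected either way.
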